Even rarer in the literature is the role of antiestrogen therapies as a form of control of this neoplasia. Case reports point to antiproliferative activity of tamoxifen in patients with NET and, in some cases, patients presenting more than 12 months of disease control.¹¹ Reports of control of carcinoid syndrome and even regression of associated retroperitoneal fibrosis have also been described.^{12,13,14} However, the only study to assess the activity of tamoxifen in neuroendocrine tumors dates back to 1984. Sixteen patients were evaluated clinical benefit in only 19 percent of cases and no radiological response. However, in this study, no patient was previously selected for HR tumor expression or degree of differentiation, which we believe limited benefit in disease control.¹⁵

Therefore, based on the premise that there is a need for research and treatment strategies for this rare neoplasm; there is clear therapeutic embezzlement in the SUS due to the high cost of the treatments approved in the country for this neoplasia; NET are tumors that may present positivity to estrogen and / or progesterone receptors; evidence points to the possibility of antiproliferative effect using hormonal therapy, we propose a phase II study of tamoxifen for patients with well differentiated NET and positive for HR, estrogen and / or progesterone expression.

Hypotheses:

Primary: Tamoxifen, an estrogen receptor agonist, exerts antitumor action in patients with well differentiated NET and positive for the expression of HR, estrogen and / or progesterone.

Secondary:

(1) Tamoxifen will promote reduced levels of chromogranin A and / or specific hormones in biochemically active tumors;

(2) The toxicity profile of tamoxifen will be compatible with the toxicity profile described in the literature.

Purposes:

Primary: To evaluate the efficacy of tamoxifen in patients with well-differentiated NETs, with HR, estrogen and / or progesterone expression, and progression.

Secondary: (1) Evaluate progression-free survival; (2) Evaluate biochemical response; (3) objective response rate; (4) disease control rate according to HR expression intensity and primary site; (5) toxicities

Exploratory:

(1) To evaluate variation of intensity and number of sites capturing PET-CT gallium-68 with tamoxifen;

(2) Document the presence of circulating tumor cells (CTC) and possible diagnostic role, such as liquid biopsy.

Outcomes:

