Primary: Disease control rate at 24 weeks after initiation of tamoxifen (since day 1 cycle 1), defined by absence of radiological progression in conventional imaging

examinations by RECIST 1.1 (Appendix I). Isolated increase of biomarker (chromogranin A) or specific hormone will not be considered progression.

Secondary:

(1) Progression-free survival, defined by time from tamoxifen day 1 cycle 1 to death from any cause or radiological progression by RECIST 1.1, whichever occurs first. Patients alive and without progression at the time of study analysis will be censored for time-to-event analysis.

(2) Biochemical response will be defined by at least 30 percent drop in the marker (chromogranin and / or specific hormone) at any time of treatment in relation to pre-treatment value (s).

(3) Radiological response rate by RECIST criteria 1.1 during the study period.

(4) Disease control rate, defined by absence of radiological progression by RECIST 1.1 criteria, according to the intensity of expression by immunohistochemistry (IHC) of HR and also according to primary site (pancreas, gastrointestinal or lung) during the study period.

(5) Toxicities frequency: Adverse events of grades 2 or more by Common Adverse Event Toxicity Criteria (CTCAE) version 5.0 during the study period.

Exploratory:

(1) Evaluate possible variations in intensity and number of sites between PET-CT gallium-68 pre-treatment and 12 weeks after initiation of tamoxifen as a continuous variable for each capture lesion. Although this examination is part of the evaluation routine of NET, in this study we will evaluate differences in the intensity of uptake with tamoxifen.

(2) Evaluate the percentage of CTC positivity in NET, as well as average number of cells in case of positivity. To evaluate the presence of estrogen and progesterone receptors in CTC.

Methodology:

Study design:

A single-arm, unicentric, single-stage clinical study of tamoxifen for patients with well differentiated neuroendocrine tumors and radiological progression with positive (> 1 percent) HR (estrogen and / or progesterone) expression by IHC.

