Patients eligible for the clinical and radiological criteria and signing the Informed Consent Form (ICF) will have the biopsy material (tumor stored in paraffin) evaluated for IHC of HR. If the expression is positive, eligibility will be complete and patients will receive tamoxifen continuously until radiological progression by RECIST 1.1, unacceptable toxicity or withdrawal of consent. If the expression for HR is negative, the patient will be informed of their ineligibility for this study and will continue to be treated by the Clinical Oncology team without any detriment to their care.

Patients will be followed up by the study team for assessments of:

(1) Safety: first in 3 weeks after tamoxifen day 1 cycle 1, and then every 6 weeks from tamoxifen day 1 cycle 1 for anamnesis with active questioning of disease symptoms and possible adverse events, physical examination and routine laboratory routine (hemogram, biochemistry, liver and renal function);

(2) Efficacy: patients will perform imaging (chest, abdomen and pelvic tomography or abdominal and pelvic resonance imaging) at baseline or pre-treatment and every 12 weeks until progression or intolerance / exit from the study. The image response evaluations will be through RECIST 1.1. For evaluation of the biochemical response, patients will undergo hormonal dosing with serum chromogranin A and specific hormones in cases of functioning NET (eg 5-HIAA dosing in 24-hour urine) at the baseline and every 12 weeks until progression (increased chromogranin and / or the functioning hormone will not be characterized as disease progression if imaging shows progression).

(3) Exploratory assessment: Patients will be assessed for somatostatin receptor expressiveness by the functional examination of PET-CT Gallium-68, which will be performed before treatment and at week 12. This evaluation, because it is exploratory, does not will be part of the definition of disease progression.

Also as an exploratory analysis, a blood sample will be collected to search for circulating tumor cells at the baseline visit (a collection only).

After a period of one year, the consultations laboratory and imaging examinations will be performed every 12 weeks until the disease progresses. Collection and evaluation times are summarized in the Table of Procedures (TABLE 1).

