For immunocytochemistry and for protein expression analysis, the spots of the membranes will be cut and placed in 24-well plates. Each spot will be hydrated with Tris Buffered Saline (TBS) for 10 minutes. Cells will be permeabilized with 0.2 percent Triton X-100 TBS for 5 min at room temperature. After a further TBS wash, the membranes will be incubated for 15 minutes in the dark and at room temperature with a 3 percent solution of hydrogen peroxide, and washed again with TBS. Then the antibodies to be screened will be applied to the spots and incubated for one hour. For the negative control, the primary antibody will be omitted. The development will be done with Dual long HRP system (Dako™) and Diaminobenzidine chromium 3,3 '(DAB) (Dako™). For reading, the spots will be stained with hematoxylin for 1 minute and adhered to the slides with aqueous mount medium. The CTC will be characterized according to the following criteria: nuclear size equal to or greater than 16µm, nuclear contour irregularity, presence of visible cytoplasm, high nucleus-cytoplasm ratio (> 0.8), as described by KREBS et al .19 When any of the criteria described are missing, the cells will be classified as atypical. The results will be given in CTC number per mL of blood.

Methodology for the PET-CT scan with Gallium-68 for the detection of somatostatin receptors

The PET-CT scan with gallium 68 to investigate somatostatin receptors will be performed using the Gemini PET-CT equipment (PET-CT-Dedicated) after administration of 0.1mCi of ⁶⁸Ga-DOTATATE, as already performed in the routine of AC Camargo as a staging method for NET. The images will be started in the minimum interval of 30 minutes and maximum of 60 minutes after the dose. CT - Helicoidal: contiguous anatomical tomographic sections 2.5 mm thick (without intravenous contrast) throughout the body (cranial, thoracic, abdominal, pelvic and lower limb segments). The Standard Uptake Value (SUV) calculation or standard capture value performed for clinically significant areas.

Study population:

Elegibility:

Research participants will be recruited from Clinical Oncology outpatient clinics and must meet all criteria below Inclusion and none of Exclusion:

Inclusion criteria

- Age greater than or equal to 18 years

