For evaluation of efficacy, patients will perform imaging (chest tomography, abdomen and pelvis or abdominal and pelvic resonance) at baseline and every 12 weeks until progression or intolerance. Patients will also be evaluated for signs and symptoms that may be related to disease progression. Patients who present clinical progression at the investigator's judgment, but without radiological progression, may discontinue treatment with tamoxifen and continue imaging until progression; however, if new treatment is instituted, the last date of receipt of tamoxifen will be the date of censure in the analysis of progression-free survival.

Patients will also be evaluated for somatostatin receptor expressiveness through the functional examination of PET-CT Gallium-68, which will be performed before treatment and at week 12, in addition to biochemical response through the dosage of chromogranin A and / or specific hormone every 12 weeks, in conjunction with imaging (tomography and / or resonance). An interval of +/- 5 days will be

allowed for imaging and PET-CT Gallium-68 exams. Patients with suspected progression (eg worsening of symptoms) may perform images within less than 12 weeks to assess progression of disease, at the discretion of the investigator.

After documentation of progression or exit from the study for other reasons, patients will be followed up by the investigator or other oncologist from the Clinical Oncology team for symptom control, imaging monitoring and possible future therapies. The patient continues to be cared for at the AC Camargo Cancer Center, if desired.

Other concomitant medications

In general, concomitant medications and therapies deemed necessary for the intensive treatment and safety of the patient are permitted provided that their use is documented in the patient's records and in the appropriate clinical record. Tamoxifen may have drug interaction with coumarin anticoagulants (Marcoumar, Marevan, Coumadin) and those with some of the new anticoagulants (Pradaxa, Xarelto). These drugs should be avoided during the study (moderate contraindication). Concomitant administration of investigational medicinal products is not permitted. Administration of any other anticancer agents including chemotherapy, target therapy and biological agents is not permitted.

Statistical Considerations

Statistical plan

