Descriptive statistics will be used to report the results of categorical and continuous variables. The time-to-event variables will be reported in medians and Kaplan Meyer curves. The degrees of toxicity will be tabulated. The number of patients discontinuing treatment due to toxicity will be presented.

Efficacy and toxicity analyzes will be performed by intention to treat. Patients receiving at least one dose of tamoxifen will be evaluated for toxicity and efficacy.

Inferential analyzes of the primary outcome according to primary site and IHC HR expression intensity will be conducted to depend on the number of cases per subgroup; if possible, these analyzes will be performed with the chi-square test. The analyzes of intensity of uptake intensity to PET-CT gallium-68 will be with paired T-test. The CTC analysis will be presented in a descriptive way.

Sample Size Calculation

To calculate the sample size, we considered the disease control rate H0 at 6 months of 50 percent (placebo arm result of the phase III studies) 5,23 and H1 as a 6 months disease control rate of 70 percent. A 10 percent bitailed type I error was considered, 80 percent power loss and 30 percent follow up loss. With these calculations, the sample number will be 22 patients.

Recruitment and Study Duration

At the AC Camargo Cancer Center, 30 patients with advanced NET are treated annually. Therefore, considering the patients already under treatment and the possible candidates without previous treatment and that out of every 10 patients, N = 4 will meet eligibility criteria (NETs with positive HR), we estimate to recruit the study population in a maximum period of 3 years and have the first full evaluation in 3 ½ years.

Ethical Considerations

The study will be conducted in accordance with the protocol, Good Clinical Practice guidelines of the International Conference on Harmonization (ICH GCP) and applicable local laws and regulatory requirements. The Free and Informed Consent Term (ICF) must be in accordance with ICH GCP guidelines, local regulatory regulations, and legal requirements. See Appendix 2 for ICF.

The investigator should ensure that each study patient, or his / her legal representative, is fully informed about the nature and objectives of the study and

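### The gallium-68 PET paired t-test has no stated unit of analysis; if the pairs are lesions, lesions of one patient are treated as independent and the error is understated

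*Combined protocol and SAP*

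**What the plan says.** The whole analysis specification is one sentence in Statistical Considerations, Statistical plan: "The analyzes of intensity of uptake intensity to PET-CT gallium-68 will be with paired T-test". It names neither the patient nor the lesion as the pair.

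Other sections bear on the unit:

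- **Purposes, Exploratory (1):** "To evaluate variation of intensity and number of sites capturing PET-CT gallium-68 with tamoxifen". The number of sites is itself of interest.
- **Outcomes, Exploratory (1):** the comparison is between the baseline scan and the scan "12 weeks after initiation of tamoxifen as a continuous variable for each capture lesion". This is the only place that gives the level of the variable, and that level is the lesion.
- **Efficacy and Follow-Up Assessment:** patients are assessed by the "functional examination of PET-CT Gallium-68, which will be performed before treatment and at week 12", that is, two scans per patient. The exploratory assessment under Study design describes the same schedule.
- **Methodology for the PET-CT scan:** the SUV is a "standard capture value performed for clinically significant areas". No mean, maximum or other per-patient summary is defined. On timing: "The images will be started in the minimum interval of 30 minutes and maximum of 60 minutes after the dose".
- **Study design, exploratory assessment:** "This evaluation, because it is exploratory, does not will be part of the definition of disease progression".

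No section mentions a mixed model, a clustered standard error or any other handling of several lesions per patient.

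**The concern.** A paired t-test takes the paired differences as independent. Applied to a variable defined per lesion, it would count each lesion as a separate piece of evidence.

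Lesions of one patient may well change together, for two reasons:

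- All lesions on a scan share that scan's uptake time. The protocol allows 30 to 60 minutes, and the time may differ between a patient's two scans.
- Patients may differ in how they respond to tamoxifen, which moves all of one patient's lesions in the same direction.

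If changes are positively correlated within patients, the pooled test uses a standard error that is too small. The confidence interval is then too narrow, and a chance shift in uptake is declared a change too often. If the patient is the intended unit, the plan still lacks a rule for reducing several lesions to one value, and that rule could be chosen after the data are seen.

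The stakes are confined to an exploratory aim. The primary outcome, the secondary outcomes and the definition of progression do not use the PET result.

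**Working it through.** **No figure to reproduce.** The plan gives no sample size, standard deviation, effect size or significance level for the PET comparison.

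**Inputs from the documents.** 22 patients and 30% loss to follow-up (Sample Size Calculation), so 22 × 0.7 = 15.4, or about 15 patients with both scans.

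**Assumptions, not in the documents.** Lesions per patient m = 1, 3, 5 or 10, the same for every patient; correlation ρ of lesion changes within a patient = 0, 0.1, 0.3 or 0.5; normally distributed changes; nominal two-sided 5%. The plan's 10% two-sided level is stated for the sample size only.

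**Formula.** With n patients, m lesions each and variance σ² of a lesion change, the mean change has variance σ²[1 + (m − 1)ρ]/(nm). The pooled t-test uses approximately σ²/(nm). Its standard error is therefore too small by the factor √[1 + (m − 1)ρ], and the approximate rejection rate with no true change is 2[1 − Φ(1.96/√(1 + (m − 1)ρ))].

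- *m = 3, ρ = 0.1:* 1 + 2 × 0.1 = 1.2; factor 1.095; 1.96/1.095 = 1.79; rejection about 7.4%.
- *m = 3, ρ = 0.3:* 1 + 2 × 0.3 = 1.6; factor 1.265; 1.96/1.265 = 1.55; rejection about 12.1%, so a nominal 95% interval covers about 88%. The 66 lesion pairs are worth 66/1.6 = 41.25.
- *m = 5, ρ = 0.5:* 1 + 4 × 0.5 = 3.0; factor 1.732; 1.96/1.732 = 1.13; rejection about 25.8%, coverage about 74%. The 110 pairs are worth 110/3 = 36.7.

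**Simulation.** False-positive rate of the pooled lesion-level t-test, 22 patients, 10,000 runs per setting:

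| Lesions per patient | ρ = 0 | ρ = 0.1 | ρ = 0.3 | ρ = 0.5 |
|---|---|---|---|---|
| 1 | 4.9% | 4.8% | 5.1% | 4.9% |
| 3 | 5.3% | 7.5% | 12.1% | 16.5% |
| 5 | 4.9% | 9.8% | 19.0% | 26.8% |
| 10 | 4.9% | 15.3% | 30.4% | 41.6% |

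A longer simulation (100,000 trials) gave 12.0% for m = 3, ρ = 0.3 and 26.3% for m = 5, ρ = 0.5. With 15 patients it gave 12.3% and 26.4%, so losing patients hardly alters the problem.

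**Alternatives under the same conditions.**

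- *Paired t-test on one mean change per patient:* 4.5% to 5.5% in every setting of the 10,000-run simulation.
- *Random-intercept mixed model fitted by REML, 22 patients, 8,000 trials:* with a t reference on 21 degrees of freedom, 4.7% (m = 3, ρ = 0.3) and 4.8% (m = 5, ρ = 0.5). With a normal reference, 6.3% and 6.1%. At ρ = 0 the t reference is conservative: 3.6% (m = 3) and 2.9% (m = 5).

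**The case against.** The strongest reply is that an omission has been shown, not an error. Recording uptake per lesion and then summarising per patient is compatible with everything written. The scan schedule does not settle the unit, and plural words such as sites and areas do not prove several lesions per patient. This stands, and it is why the point is conditional. The plan is incomplete under either reading, however: with lesions as pairs it ignores clustering, and with patients as pairs it has no summary rule.

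Second, nothing rests on the result. The aim is exploratory and no significance threshold or claim is attached to it. This also stands and sets the priority. Even so, the plan prescribes an inferential test here, while it leaves the circulating tumour cell analysis descriptive. A test needs a stated independent unit.

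Third, the size is wholly assumed. No section says that the uptake-time window alters SUV, or by how much, and at low correlation the inflation is modest (7.5% for 3 lesions at 0.1). That is correct. Only the direction is certain, and only when the correlation is positive and patients contribute several lesions.

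Fourth, the per-patient test has limits. Lesions that appear or vanish by week 12 have no pair. With unequal lesion counts, a patient mean and a mixed model can weight patients differently. With skewed patient changes (assumed mean-centred lognormal, sigma 0.5, 0.75 and 1, 22 patients), the patient-level t-test itself rejects 6.8%, 9.2% and 13.0% at nominal 5%. These caveats are real and belong in the specification. Unpaired lesions and skew are problems for the plan's own test too, so they are no reason to leave the unit unstated.

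**Conclusion.** The concern holds in its conditional form. The plan does not state the unit of the PET paired t-test. Its outcome definition points to lesions, and it provides nothing for several lesions per patient. If lesions are pooled and their changes are positively correlated within patients, the standard error is too small, by a factor of 1.26 at 3 lesions and correlation 0.3, and 1.73 at 5 lesions and 0.5. These factors apply when every patient has the same number of lesions. Over the multi-lesion settings tried with correlation 0.1 to 0.5, the false-positive rate runs from about 7% to 42% against a nominal 5%. There is no inflation with one lesion per patient or zero correlation. All of these figures are illustrations that rest on assumed lesion counts, correlations and test level. The consequence is limited to an exploratory aim, so this is an improvement that could be made, not one on which the trial depends.

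**What to change.** In the Statistical plan, name the patient as the unit and apply the paired t-test to one pre-specified summary change in SUV per patient, for example the mean over that patient's lesions. This gives at most 22 differences. The same text should say which lesions enter the summary and how lesions seen on only one of the two scans are handled.

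Alternatively, keep the lesion changes and fit a linear mixed model with a random patient effect, using a t reference with about (patients − 1) degrees of freedom. Since the two can weight patients differently, name one of them in advance.

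The cost is a sentence or two of text and no new data. The interval will usually be wider than the pooled one. For the patient-mean test it is about 1.31 times as wide at 3 lesions and correlation 0.3, 1.82 times at 5 lesions and 0.5, and 1.03 to 1.04 times at zero correlation. Where the correlation is positive, most of that width is uncertainty the pooled test leaves out. A per-patient mean weights patients equally, not lesions. Strong skew in patient changes would remain a limitation and should be inspected when the result is reported.

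### The stated inputs require about 37 evaluable patients (53 enrolled), not 22; with 22 the power against a 70% disease control rate is 49% by exact test and at most 67% by score test, before any loss

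*Combined protocol and SAP*

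**What the plan says.** The study is described under Study design as "A single-arm, unicentric, single-stage clinical study of tamoxifen for patients" with hormone-receptor-positive, well-differentiated neuroendocrine tumours. The primary outcome is binary: "Disease control rate at 24 weeks after initiation of tamoxifen", meaning no radiological progression by RECIST 1.1.

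The Sample Size Calculation sets the null rate at 50%, taken from placebo arms of phase III studies, and the alternative at 70%. It adds: "A 10 percent bitailed type I error was considered, 80 percent power loss and 30 percent follow up loss". It then states: "With these calculations, the sample number will be 22 patients". It gives no formula and does not say whether 22 is before or after the loss allowance.

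The Statistical plan section specifies intention-to-treat analysis and says: "Patients receiving at least one dose of tamoxifen will be evaluated for toxicity and efficacy". The only tests it names are for subgroup comparisons of the primary outcome ("if possible, these analyzes will be performed with the chi-square test") and a paired t-test for PET-CT uptake. It gives no test and no success threshold for the primary outcome in the whole cohort.

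**The concern.** All the ingredients of a one-sample binomial calculation are given, so the result can be checked. Detecting 70% against 50% with 5% in the upper tail and 80% power normally takes well over 30 patients before any allowance for loss. A total of 22 that is said to include 30% loss leaves only about 15 evaluable.

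The stated power governs how a negative result is read. A reader who believes the 80% will take a failure to exceed 50% as fairly strong evidence that tamoxifen does not reach 70% disease control. If the real power is near one half, that inference fails.

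The missing success rule makes this worse. At n = 22, an observed 15 successes is significant by one common test and not by another, so the conclusion could depend on a choice made after the data are seen.

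**Working it through.** **Inputs.** From Sample Size Calculation: p0 = 0.50, p1 = 0.70, alpha 10% two-sided (5% in the upper tail), power read as 80%, loss 30%, stated N = 22. From Study design and Outcomes: one arm, one stage, binary endpoint at 24 weeks.

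**1. Attempt to reproduce 22.** One-sample score formula:

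n = [(z0.95 × √(p0·q0) + z0.80 × √(p1·q1)) / (p1 − p0)]²
= [(1.645 × √0.25 + 0.842 × √0.21) / 0.20]²
= [(0.8225 + 0.3859) / 0.20]² = 36.5, so **37 evaluable**.

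With 30% loss: 37 / 0.70 = 52.9, so **53 enrolled**.

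Other standard methods with the same inputs:

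| Method | Evaluable | Enrolled (÷ 0.70) |
|---|---|---|
| Wald (variance under 70%) | 33 | 48 |
| Arcsine | 37 | 53 |
| Null variance | 39 | 56 |
| Continuity-corrected | 42 | 60 |
| Exact binomial, smallest n with 80% power | 37 | 53 |

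The exact rule at 37 is success at 24 or more: P(X ≥ 24 | 0.5) = 0.049 and P(X ≥ 24 | 0.7) = 0.807. Exact power is saw-toothed in n and stays at or above 80% only from 42 evaluable.

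Numbers near 22 appear only when stated inputs are changed. A one-sided 10% Wald calculation with no loss allowance gives 24. A one-sided 20% Wald calculation gives 15, or 22 after loss. Dropping the power term from the two-sided 10% Wald formula also gives 15, or 22 after loss. Reading the power clause literally as 20% power gives 5, or 8 with loss.

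**2. What 22 evaluable patients deliver.**

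| Success rule | Basis | P(success given 50%) | Power at 70% |
|---|---|---|---|
| ≥16/22 | exact, upper tail ≤5% | 0.026 | 0.494 |
| ≥15/22 | uncorrected score, z = 4/√5.5 = 1.706 > 1.645 | 0.067 | 0.671 |
| ≥14/22 | needed to reach 80% power | 0.143 | 0.814 |

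The ≥15 rule has a true two-sided error of 2 × 0.067 = 13.4%, above the stated 10%, so 67% is an upper bound. Reaching 80% power with 22 patients means accepting an upper-tail error of 14.3%, nearly three times the 5% planned.

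**3. After loss, analysing completers only.** 22 × 0.70 = 15.4.

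- n = 15: exact ≥12, power 0.297; score ≥11 (z = 1.807), power 0.515.
- n = 16: both tests ≥12 (z = 2.0), power 0.450.
- Averaged over a Binomial(22, 0.7) number of completers, resetting the rule each time: 0.389 exact, 0.478 score.

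**4. After loss, counting lost patients as failures** (assuming loss is unrelated to outcome). The success probability becomes 0.70 × (1 − loss).

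- 10% loss, p = 0.63: power 0.238 at ≥16/22, 0.396 at ≥15/22.
- 30% loss, p = 0.49: power 0.021 at ≥16/22, 0.056 at ≥15/22.

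**5. The 15/22 case.** The score test rejects 50% (z = 1.706). The 90% Clopper-Pearson lower limit is 48.5%, which does not exclude 50%. At 16/22 the interval is 53.2% to 87.4%, so rule and interval agree.

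**The case against.** The strongest objection concerns power after loss. Disease control is defined as absence of radiological progression and every dosed patient is evaluated, so a patient lost without documented progression could be counted as controlled. With 30% loss unrelated to outcome, the success rate under the alternative becomes 0.30 + 0.70 × 0.70 = 0.79, and power is 0.84 at ≥16/22 and 0.93 at ≥15/22. The documents do not exclude this reading. But the null rate then becomes 0.30 + 0.70 × 0.50 = 0.65, and the chance of a false success rises to 0.30 and 0.47. That is not 80% power at the stated 10% level, so it does not rescue the figure of 22.

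A second objection is that the exact test is conservative, using 2.6% of the 5% tail. A mid-p test gives 0.047 at 15/22 and would keep 67% power. This is fair: the documents do not dictate a test. A mid-p or score rule has a true upper-tail size of 6.7%, however, and still falls short of 80%.

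Third, a small single-centre study in a rare tumour may have good reason to stop at 22. On the plan's own recruitment figures, 30 patients a year × 3 years × 4 in 10 = 36 eligible, plus patients already under treatment; 53 enrolled looks out of reach unless that second group is large. This may justify the size, but not attributing 80% power to it. Nor does omitting the loss allowance because all dosed patients are analysed: about 37 would still be needed.

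**Conclusion.** The paragraph is wrong as written. Its inputs lead to about 37 evaluable and 53 enrolled, and 22 falls short whether it means enrolled or evaluable. With no loss, the risk of missing a true 70% rate is 51% (exact) or 33% (score), against the implied 20%. With 15 or 16 completers it is about 48% to 70%. If lost patients count as failures it is higher still.

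This rests on reading the garbled power clause as 80% power, and on a one-sample binomial comparison, which the design and endpoint imply. The figures with lost patients counted as failures also assume that loss is unrelated to outcome. How 22 was obtained is not documented. The error does not bias the estimated disease control rate; it misstates what the study can conclude about its only primary endpoint.

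**What to change.** Restate the sample-size paragraph so that its figures agree, without enrolling more:

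- Keep 22 patients and the two-sided 10% level.
- Name the primary analysis in the Statistical plan section: an exact binomial test of 24-week disease control against 50%, success at 16 or more of 22, reported with the matching 90% Clopper-Pearson interval.
- State power against 70% as 49% with 22 evaluable, and about 30% to 45% with 15 or 16 evaluable (12 successes needed at either number).
- Say how a treated patient with no 24-week status is counted, and whether 22 already includes the 30% loss allowance.

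If the sponsor prefers another test, it should be named in advance with its threshold, true error rate and power.

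The cost is one reworded paragraph and two or three added lines. The price is candour: stated power falls from 80% to 49% or less, and lower again if patients with missing status count as failures.
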